12.1.2 Safety analysis set

All patients who receive at least 1 dose of randomized investigational product, and for whom any post-dose data are available will be included in the safety analysis set. Safety results will be grouped according to randomization, and not the actual dose taken.

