Revised Clinical Study Protocol

Drug Substance	AZD1656
Study Code	D1020C00009
Edition Number	2
Date	

A 4-Month, Randomized, Double-Blind, Placebo- and Active-Controlled, Multi-Centre, Parallel-Group Study, with an Optional 2-Month Extension, to Evaluate Efficacy, Safety and Tolerability of AZD1656 as Add-on Treatment to Metformin in Type 2 Diabetes Mellitus Patients

Sponsor:

AstraZeneca AB, [name].

This submission /document contains trade secrets and confidential commercial information, disclosure of which is prohibited without providing advance notice to AstraZeneca and opportunity to object.

The following Amendment(s) and Administrative Changes are included in this revised protocol:

Amendment No.	Date of Amendment	Local Amendment No.	Date of local Amendment
_____	_____	_____	_____
_____	_____	_____	_____
_____	_____	_____	_____
Administrative change No.	Date of Administrative Change	Local Administrative change No.	Date of local Administrative Change
_____	_____	_____	_____

PROTOCOL SYNOPSIS

A 4-Month, Randomized, Double-Blind, Placebo- and Active-Controlled, Multi-Centre, Parallel-Group Study, with an Optional 2-Month Extension, to Evaluate Efficacy, Safety and Tolerability of AZD1656 as Add-on Treatment to Metformin in Type 2 Diabetes Mellitus Patients

Study centre(s) and number of patients planned

This study will be conducted in approximately 130 study centres in 12 countries in Europe, South America and Mexico. It is planned to have approximately 540 patients in totally 7 arms. One arm with open-label AZD1656 up to 90 patients, 4 arms with approximately 90 patients randomized per arm and 2 “fixed dose” arms with approximately 45 randomized patients per arm.

Study period		Phase of development
Estimated date of first patient enrolled	Q4 2009	Phase II
Estimated date of last patient completed	Q1 2011	

Objectives

Primary objective

- The primary objective is to compare the effect on glucose control of 4 different AZD1656 dosing regimens with placebo in type 2 diabetes mellitus patients on metformin treatment, as evaluated by the difference in HbA1c between baseline and final visit at 4 months.

Secondary objectives

- To characterise the population pharmacokinetic and pharmacodynamic properties of AZD1656 in type 2 diabetes mellitus patients treated with metformin by utilisation of non-linear mixed effects modelling methodology.

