2.2 Secondary objectives

- To characterise the population PK and PD properties of AZD1656 in type 2 diabetes mellitus patients treated with metformin by utilisation of non-linear mixed effects modelling methodology.
- To evaluate other variables of glucose control (fasting plasma glucose, mean daily self-monitored plasma glucose [7-point measurements], oral glucose tolerance test data and number of responders in terms of HbA1C $\leq 7\%$ and $\leq 6.5\%$, respectively) after 4 months in patients receiving AZD1656 as add-on treatment to metformin compared to placebo as add-on treatment to metformin.
- To evaluate other cardiovascular risk factors, such as total cholesterol, low-density lipoprotein cholesterol, high-density lipoprotein cholesterol, triglycerides and c-reactive protein, after 4 months in patients receiving AZD1656 as add-on treatment to metformin compared to placebo as add-on treatment to metformin.
- To investigate the safety and tolerability of AZD1656 compared to placebo, glipizide by assessments of adverse events occurring during the study (including hypoglycaemic events), blood pressure, pulse, physical examination, body weight, safety laboratory variables and electrocardiogram.
- To explore the safety and tolerability of AZD1656 in patients with severely impaired glucose control during a 4 months treatment period.

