3.1 Overall study design and flow chart

[figure not shown]
This will be a 4-month, randomized, double-blind, placebo- and active-controlled, multi-centre study of AZD1656 as add-on therapy to metformin compared to placebo, in approximately 540 T2DM patients. Glipizide will be included in separate treatment arm as add-on treatments to metformin. After 4 months, an optional 2 months extension will follow. The study consists of 7 parallel arms with 90 patients in each arm except for the 2 fixed dose arms with AZD1656 that will consist of 45 patients in each arm.

The study includes 2 cohorts of patients, see [Figure 1](#). In the main treatment cohort (cohort 1) patients can be randomized to one of 6 different treatment arms with AZD1656, glipizide or placebo. Patients in this cohort should have HbA1c between $\geq 7.5\%$ and $\leq 10\%$ at enrolment. The patients will be randomized to 1 of 4 different dose regimens of AZD1656 (a minimum dose of 10mg daily titrated to maximum dose of 140mg daily, a minimum dose of 20mg daily titrated to a maximum dose of 200mg daily, 20mg daily or 40mg daily fixed doses), an glipizide regimen of glipizide (minimum dose of 5mg daily to a maximum dose of 20mg daily) or placebo, as add-on to an unchanged dose of metformin. The double-blind AZD1656/glipizide/placebo will be given twice daily.

Cohort 2:

In cohort 2, up to 90 eligible patients with HbA1c between $>10\%$ and $\leq 12\%$ at enrolment will be assigned (no randomization) to an open-label treatment with AZD1656, which will be titrated from 20mg up to 200mg. For safety reasons, patients in cohort 2 must meet all eligibility criteria and after the initial titration period, the same criteria for hyperglycaemic rescue medication will apply also in this cohort. Recruitment will be completed regardless of reaching the number in the open-label AZD1656 arm. The termination of the recruitment will be linked to cohort 1 (450 randomized patients).

Figure 1 Study design overview

Target patient population is T2DM patients not adequately controlled on maximum tolerated metformin dose ($\geq 1500\text{mg}$) as single therapy and with stable metformin treatment for at least 10 weeks prior to enrolment (screening).

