3.1.1 Study visits

Visit 1 (Enrolment visit)

At the enrolment visit 18 to 28 days before randomization and after written informed consent is given, eligible patients will enter the study. Each patient will be allocated a strictly sequential enrolment code (E-code) by accessing the IVRS/IWRS system.

The following enrolment assessment will be performed: demography, relevant medical and surgical history, smoking history, alcohol use, physical examination, ECG, vital signs (BP and pulse), weight and height, concomitant medications.

All patients need to be fasting, see Section 5.1. A safety laboratory screen will be done by central lab. Additional blood samples will be taken such as FPG, HbA1c, Insulin, C-peptide. For women whose last menstruation was >1 year ago, serum FSH and LH will be tested to ensure that they are within the postmenopausal range.

Visit 2 (Run-in period)

At visit 2, eligible patients will be switched to the study metformin, but keeping their initial dose unchanged. Patients will be given a Patient Diary and receive glucometers for self-monitored plasma glucose (SMPG). For more information on SMPG see section 3.1.2. A fasting morning plasma glucose and a bed-time plasma glucose assessment are needed on a daily basis from the run-in period until the end of the titration period. At this visit, patients do not need to be fasting.

Visit 3 (Randomization visit)

At visit 3, eligible patients will be randomized to study medication (AZD1656, glipizide or placebo treatment) via the IVRS/IWRS system. The eligible patients in cohort 2 will be assigned (no randomization) to an open-label treatment with AZD1656. Patients will be fasting and undergo a physical examination, a safety laboratory screen, ECG, vital signs (BP and pulse), weight, waist and hip circumference measurement and concomitant medications. Advice will be given for diet and life style during the visit. Additional blood samples will be taken such as FPG, HbA1c, Insulin, C-peptide, Lipids and CRP. The OGTT test will be performed in a subgroup of patients.

The patient diary will be reviewed for compliance. The site will check that the patient has taken their metformin as planned. The first dose of the study medication will be taken together with breakfast at the site or at home/work. The investigator will also record if any Adverse Event (AE) occurred since the last visit.

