5.2.1 Procedures for enrolment/randomization

Procedures for enrolment

The Principle Investigator or delegate will:

- Obtain signed informed consent from the potential patient before any study-specific procedures are performed.
- Assign potential patients with a unique enrolment number, beginning with E....001.

Procedures for randomization

The Principle Investigator or delegate will:

- Determine patient eligibility (see Section 4).

- Assign eligible patients with a unique randomization code (patient number) through IVRS/IWRS.

Patients who satisfy the entry criteria at Week 0 (Visit 3) will be randomized to receive either AZD1656 (10mg daily titrated to maximally 140mg daily, 20mg titrated to maximally 200mg daily (blinded or open), 20mg daily or 40mg daily fixed dose), placebo or glipizide (5mg daily titrated to maximally 20mg daily) in combination with background metformin. The randomization scheme will be generated by AstraZeneca, using the global randomization system (GRand). Randomization codes will be assigned as patients become eligible for randomization and each patient will be assigned a unique randomization code.

Nobody outside the group generating the randomization scheme will have knowledge of the scheme. Hence, investigators will have no knowledge beforehand of the treatment the patient will receive. If a patient is provided incorrect treatment by mistake (ie, treatment not consistent with that assigned by ICOPhone IVRS/IWRS), attempts should not be made to remedy the error once study medication has been dispensed and ingested by the patient. An ICON Clinical Research representative should be immediately notified as soon as any error is discovered, in order to determine the patient status (ie, allowance to continue or need for immediate withdrawal). If a patient is provided with the wrong treatment, this will be noted as a protocol violation, regardless of whether the patient is allowed to continue or not.

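### The safety set is written for randomized product and randomized groups, so read literally it has no place for the non-randomized open-label cohort and keeps misdispensed patients under the arm they did not take

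*Protocol*

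**What the plan says.** Protocol section 12.1.2 fixes both membership and grouping of the safety set. On membership: "All patients who receive at least 1 dose of randomized investigational product, and for whom any post-dose data are available will be included". On grouping: "Safety results will be grouped according to randomization, and not the actual dose taken". Section 12.2.7 summarises safety on this set and on the same set with post-rescue data removed. No other safety set is defined. Section 12.2.10 carries the same approach into the extension.

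For cohort 2, section 3.1 says that eligible patients "will be assigned (no randomization) to an open-label treatment with AZD1656, which will be titrated from 20mg up to 200mg". Section 3.1.1 repeats this for Visit 3: "The eligible patients in cohort 2 will be assigned (no randomization) to an open-label treatment with AZD1656". The synopsis agrees. One secondary objective in section 2.2 concerns this cohort: "To explore the safety and tolerability of AZD1656 in patients with severely impaired glucose control during a 4 months treatment period". Section 3.2 gives the same purpose as the reason for having the open arm.

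Other text is looser. Section 5.2.1 names the 20 to 200 mg regimen, in both its blinded and its open form, among the treatments to which patients are randomized. Section 5.5.2 lists the open starting dose under its randomized-treatment heading.

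On dispensing errors, section 5.2.1 says "attempts should not be made to remedy the error once study medication has been dispensed and ingested by the patient". The CRO then decides whether the patient may continue, and a protocol violation is recorded either way.

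**The concern.** A safety set should hold everyone exposed to the product and should show events against what was taken. The text in section 12.1.2 departs from this in two ways.

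- **Membership.** Patients who are not randomized do not receive randomized product and have no group according to randomization. Followed to the letter, the main summaries of adverse events, hypoglycaemia and laboratory data would leave out the cohort with the poorest glucose control, which was added largely to learn about safety there.
- **Grouping.** A placebo patient who was given AZD1656 or glipizide in error and then had a hypoglycaemic event would be counted under placebo. Mixing of this kind pulls the drug-placebo safety contrast towards no difference, which is the wrong direction for a safety comparison.

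An analysis plan may exist, but the protocol has already fixed both rules, so a plan that repaired them would be departing from the protocol.

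**Working it through.** **Head count**

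Inputs: the synopsis gives "One arm with open-label AZD1656 up to 90 patients, 4 arms with approximately 90 patients randomized per arm", plus two fixed-dose arms of about 45. Section 3.1 gives 450 randomized patients in cohort 1. The planned total is about 540.

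- Randomized: 4 × 90 + 2 × 45 = 450, as stated.
- Total: 450 + 90 = 540, as stated.
- Randomized to AZD1656: 90 + 90 + 45 + 45 = 270. With cohort 2: 270 + 90 = 360.

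Share outside the safety set on a literal reading, at the cohort's ceiling of 90:

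- of all patients: 90 / 540 = 16.7%
- of AZD1656-exposed patients: 90 / 360 = 25%
- of patients on the 20 to 200 mg titration: 90 / (90 + 90) = 50%

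**What the missing patients mean for rare events**

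If no event of a given kind is seen in n patients, the one-sided 95% upper bound on its rate is 1 − 0.05^(1/n).

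- n = 270 (AZD1656 as the set is written): 1.10%
- n = 360 (with cohort 2): 0.83%
- n = 90 (cohort 2 alone): 3.27%

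As written, the set supports no such statement for cohort 2. The pooled figure only illustrates the loss of information, since cohort 2 differs at baseline and should be shown separately.

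**Texts side by side**

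- Safety set (12.1.2): randomized product, grouped by randomization.
- Cohort 2 (synopsis, 3.1, 3.1.1): assigned, explicitly not randomized.
- Sections 5.2.1 and 5.5.2: open regimen spoken of as randomized.
- PK/PD set (12.1.3): all included patients with at least 1 dose, so a rule that does not depend on randomization was available to the authors.

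The first two cannot both be followed if cohort 2 is to be summarised. The third would let cohort 2 in by loose usage, but still gives it no randomized group.

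**Misdispensing**

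Section 5.2.1 foresees the error, rules out correcting it after ingestion and leaves open that the patient continues. Blinded product is dispensed at nine visits (3 to 10 and 12, Table 2) from 13 wallet combinations (5.5.1), so an error is possible. The protocol gives no error rate, and no size can be computed.

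**The case against.** The strongest reply is that cohort 2 was plainly meant to be included. Sections 5.2.1 and 5.5.2 and Table 2 place the open arm within the randomized treatment period, section 3.1.3 counts its product as investigational product, and section 3.1 counts it among seven arms. Section 12.2.7.1 lists adverse events per patient and summarises them by treatment group. This is probably what the sponsor intended, and it limits the point: the data would be collected and could be listed. A reader might infer that safety in cohort 2 cannot be reported at all; the documents do not support that. What they show is that no defined set or group covers the cohort, and loose wording elsewhere adds an inconsistency without resolving it.

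The second reply is that the grouping sentence speaks of dose, whereas section 12.1.1 speaks of treatment received. In titrated arms, grouping by assigned regimen and not by dose step reached is sensible, and the sentence may be aimed mainly at that. This stands in part. As written, though, the sentence makes no exception for a patient who took another arm's product.

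Two further inferences are tempting and should not be drawn.

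- **That leaving cohort 2 out of the full analysis set is also an error.** It is not. That set serves randomized comparisons with placebo, and a non-randomized open-label cohort does not belong in it.
- **That one misplaced hypoglycaemic event would change the placebo count by some stated fraction.** The four events in section 1.4.2 come from AZD1656-exposed subjects in short studies, including healthy volunteers. They give no placebo rate, and no misdispensing rate is available either.

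**Conclusion.** The point holds as a definition that conflicts with the design. Read literally, section 12.1.2 leaves up to 90 of about 540 patients, and up to a quarter of planned AZD1656 exposure, without a safety set or group, while a secondary objective depends on them. Ninety is a ceiling: section 3.1 ends recruitment on cohort 1 whether or not the open arm fills, so the shares could be smaller. The conclusion rests on taking the repeated statements that cohort 2 is not randomized at face value over the looser usage in sections 5.2.1 and 5.5.2.

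The grouping rule is a secondary defect. Its direction is clear for mix-ups between placebo and active product; mix-ups between AZD1656 regimens put events under the wrong regimen, not the wrong drug. Its size is unknown. No power or type I error figure is affected.

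**What to change.** - In section 12.1.2, define the safety set as all patients with at least 1 dose of investigational product, randomized or assigned, and any post-dose data.
- Show cohort 2 as its own group in every safety summary, including the extension.
- Group safety by the regimen actually received, not by the titration step reached.
- State a rule for patients who took product from more than one regimen. Base it on drug accountability (5.7.1) and kit identifiers (5.5.3). The interactive response system records what was assigned, and the error in question is a departure from that.
- Reconcile sections 5.2.1 and 5.5.2 with the synopsis and sections 3.1 and 3.1.1 on whether the open arm is called randomized.
- Leave the full analysis set as randomized patients only, and summarise cohort 2 glucose data descriptively for the exploratory objective in section 2.3.

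The cost is a wording change and a small amount of work to classify patients with mixed exposure. No new data are needed.

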12.1.3 PK and PD analysis set

Data from all included patients receiving at least 1 dose, contributing with at least 1 PK or PD measurement and providing reliable time-points for sampling and dose intakes, will be used for PK/PD analysis.

12.2 Methods of statistical analyses

Descriptive statistics includes n, mean, standard deviation, min, median, and max, and for variables log-transformed in the analysis, also geometric mean and coefficient of variation (CV%), for quantitative variables, and frequencies for qualitative variables.

The statistical analysis will be performed using SAS[®] version 9.1 or later.

All tests will be performed at the 5% significance level unless otherwise is stated. The study is not powered to demonstrate a statistically significant difference between glipizide and AZD1656. Nevertheless, comparisons will be performed for the comparator versus AZD1656 and placebo. For the comparison the comparator versus AZD1656, a one-sided 90% confidence interval will be calculated for the treatment effect. One-sided 90% confidence intervals for the treatment effect should also be provided for the comparison between AZD1656 and placebo.

12.2.1 Data Handling Considerations

Last observation carried forward methods (LOCF) will be used for any missing efficacy data; baseline data will not be carried forward. Analyses based on LOCF data will only be performed using the FAS.

Genotype data might be analysis if needed and a separate report will be prepared where appropriate.

12.2.2 Multiple Treatment Comparisons

For conclusion a hierarchical closed testing procedure will be adopted for the efficacy analyses. Treatment group comparisons will be tested in dose span order whereby comparisons with placebo will commence with the highest dose regimen (randomized patient on 20mg daily titrated to maximum of 200mg daily) tested first, next dose regimen 10mg daily titrated to maximum of 140mg daily, fixed dose 40mg daily and finally the fixed dose 20mg daily. Estimates of the treatment effect and corresponding 95% confidence intervals will be presented together with the p-values for the treatment effect. All tests will be performed at the 5% level of significance.

12.2.3 Demographic, baseline and background characteristics

All variables will be presented with descriptive statistics within each treatment group.

12.2.4 Concomitant Medication

Concomitant medication is defined as a medication that is taken prior or after the first day of study treatment.

For incomplete or partial concomitant medication start and/or stop dates, where it is not possible to classify the concomitant medication as before or during, using available date information, it will be assumed that the concomitant medication was taken during double blind treatment.

Concomitant medication will be summarised by treatment group for the Safety analysis set using drug class and preferred term. Patients will only be counted once within a drug class, and once for a medication.

All medication, taken both prior to and during the double blind treatment phase, will be included in the supportive data listing. A flag will be added to indicate where a medication was taken prior to the start of double blind treatment.

12.2.5 Compliance and Study Drug Exposure

The compliance of study drug will be completed for overall exposure per patient.

12.2.6 Efficacy Analysis

Individual data will be listed. Where appropriate, descriptive statistics or table of frequencies will be presented.

12.2.6.1 Primary variable

An analysis of covariance (ANCOVA) will be performed on the change in HbA1c from baseline to the final visit at 4 months, with treatment as a fixed factor and the corresponding baseline HbA1c as a covariate.

The FAS will be applied as the primary analysis set on the LOCF approach whereby for missing assessments (visits), the last observation will be carried forward. Baseline values will not be carried forward.

The PP analysis set based on Observed Case will be applied as supportive analyses to the FAS.

The following additional sensitivity analyses will be performed on the primary variable:

- Observed Case analyses will be performed on the FAS whereby missing intermediate assessments (visits) will be excluded.
- If the primary analyses are significant, an additional analysis adjusting for centre/regional effects will be conducted. The primary efficacy variable will be analysed applying the ANCOVA model including additional covariate for centre/region on both the FAS and PP analysis sets.
- Further exploratory and subgroup investigations will be performed on the primary variable considering effects of other factors including gender. Exploratory analysis methodology will be detailed further in the statistical analysis plan.

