3.1.6 Hyperglycaemia during study

After randomization, definitions of hyperglycaemia and the use of rescue medication will apply, see Section [5.6.1](#). Patients will receive written instructions on the need for plasma glucose assessments in case of hyperglycaemia symptoms, and to contact the investigator if two consecutive fasting morning plasma glucose values are >11 mmol/L (198 mg/dL). The investigator must also at every study visit consider extra plasma glucose monitoring, especially if the patient's glucose levels start to deteriorate. Patients meeting criteria for hyperglycaemia should receive treatment with basal night-time insulin in addition to metformin and the randomized IP treatment.

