12.1.1 Full analysis set

All randomized patients with at least 1 dose administered, and with at least 1 post-baseline efficacy data, will be included in the Full Analysis Set (FAS).

Patients will be analysed according to the randomized treatment, irrespective of the treatment received.

This will be the primary analysis set used for all efficacy analysis variables.

The Per-Protocol (PP) analysis set will consist of the patients in the FAS who do not violate any major entry condition and do not violate the protocol between randomization and study completion. Major deviations from the protocol procedures include:

- Violation of inclusion/exclusion criteria.
- Disallowed concomitant medication.
- Missing key efficacy data. (ie, Hb1Ac at 4 months or last visit).
- Patient is not compliant

This will be the secondary efficacy analysis set and will be applied to all key efficacy analysis variables.

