12.2.7 Safety Analysis

Safety variables will be summarised for the safety analysis set and the safety analysis set excluding post rescue treatment.

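### The efficacy rules keep glucose values measured on rescue insulin and plan no analysis without them, although post-rescue data are separated for safety; rescue handling should be stated and a supplementary analysis added

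*Protocol*

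**What the plan says.** **Rescue (protocol 3.1.6, 5.1, 5.6, 5.6.1).** "Patients meeting criteria for hyperglycaemia should receive treatment with basal night-time insulin in addition to metformin and the randomized IP treatment". Rescued patients therefore remain in the study and on the visit schedule. Rescue insulin is permitted medication under 5.1 and 5.6. Its start and dose changes are recorded in the eCRF.

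**Primary analysis (12.2.6.1, 12.2.1).** "An analysis of covariance (ANCOVA) will be performed on the change in HbA1c from baseline to the final visit at 4 months", with treatment as factor and baseline HbA1c as covariate, on the full analysis set (FAS). The imputation rule is: "Last observation carried forward methods (LOCF) will be used for any missing efficacy data; baseline data will not be carried forward".

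**Supportive analyses (12.2.6.1, 12.1.1).** "The PP analysis set based on Observed Case will be applied as supportive analyses to the FAS". The per-protocol (PP) exclusion closest to rescue is "Disallowed concomitant medication". The other listed analyses are FAS observed case, an adjustment for centre or region, and exploratory subgroup work.

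**Secondary variables (12.2.6.2).** Responders at 7% and 6.5%, FPG, SMPG and OGTT are analysed on the FAS with LOCF. No condition on rescue is attached.

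**Safety (12.2.7, and the synopsis outcome list).** "Safety variables will be summarised for the safety analysis set and the safety analysis set excluding post rescue treatment".

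**The concern.** The protocol recognises rescue as something that changes the meaning of later data, and provides a second safety set for it. It has no counterpart for efficacy, where insulin acts directly on the endpoint.

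Rescue follows from lack of effect, so if AZD1656 works, more rescue is expected on placebo and on the less effective regimens. Insulin then lowers HbA1c most where the study drug does least. That narrows both the contrast with placebo and the differences between regimens, and Section 3.2 describes this as a dose-finding study meant to support the choice of dose range for phase III. Section 12.2.2 tests the regimens in a fixed order, so a diluted first comparison that fails stops the later ones. A placebo patient who reaches target on insulin is counted as a placebo responder.

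LOCF can extend the problem. Under 5.8, patients still hyperglycaemic despite insulin are discontinued, and any HbA1c already taken on insulin is then carried to month 4.

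**Working it through.** **1. Does a post-rescue value enter each analysis?**

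| Analysis | Rule that could remove it | Result |
|---|---|---|
| FAS, LOCF (primary) | replaces missing values only | kept |
| FAS, observed case | leaves out missing visits only | kept |
| PP, observed case | disallowed medication; rescue insulin is allowed | kept on the likely reading (the deviation list is not closed) |
| Responders, FPG, SMPG, OGTT (FAS, LOCF) | none | kept |
| Safety, second set | excludes post-rescue data | removed |

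**2. The plan's own figure.** Section 12.3 gives a difference of 0.7, SD 1.4, two-sided 5% two-group t-test, 90% power and 86 per group. The non-centrality is 0.7 / (1.4 × √(2/86)) = 3.28 on 170 degrees of freedom, with critical value 1.974. Power is 0.903, so 86 reproduces. The only allowance is for drop-out: 1 − 86/90 = 4.4%. There is none for rescue.

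**3. Attenuation.** Let pP and pA be the proportions rescued before the month-4 sample on placebo and AZD1656, and r the mean extra HbA1c fall from insulin in those patients. Then

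retained difference = 0.7 − (pP − pA) × r.

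The protocol gives none of these three inputs. All values of pP, pA and r below are assumptions, and 0.7 is taken to be the effect without rescue, which Section 12.3 does not say. Power is from the noncentral t at 86 v 86, at both ends of the SD range in Section 12.3 (1.1 to 1.4).

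| pP v pA | r | Retained difference | Power, SD 1.4 | Power, SD 1.1 |
|---|---|---|---|---|
| equal | any | 0.70 | 90% | 99% |
| 20% v 10% | 0.3 | 0.70 − 0.03 = 0.67 | 88% | 98% |
| 20% v 10% | 1.0 | 0.70 − 0.10 = 0.60 | 80% | 94% |
| 30% v 10% | 0.3 | 0.70 − 0.06 = 0.64 | 85% | 97% |
| 30% v 10% | 0.5 | 0.70 − 0.10 = 0.60 | 80% | 94% |
| 30% v 10% | 1.0 | 0.70 − 0.20 = 0.50 | 64% | 84% |

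For a fixed-dose arm (45 × 86/90 = 43 evaluable, v 86), the 30% v 10% case takes power from 76% to 68%–48% at SD 1.4, and from 92% to 87%–68% at SD 1.1. The lower starting point comes from the arm size, which is a separate matter.

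**4. How long can rescue act before the endpoint?** Visit 9 is day 90 ± 5 and Visit 10 is day 120 ± 5 (Table 2). The gap is 115 − 95 = 20 to 125 − 85 = 40 days. Under the cohort 1 bullets in 5.6.1, HbA1c above 8.0% triggers rescue only after Visit 9, so insulin started on that trigger has at most about 20 to 40 days. Going from above 8.0% to 7% or below needs a fall of more than 1.0 point in that time. FPG-triggered rescue can start from baseline and act for longer. The opening sentence of 5.6.1, however, gives HbA1c above 8% after randomisation with no time limit, and cohort 1 enters at 7.5% to 10%. On that reading rescue could be early and common. The two statements conflict and must be reconciled; the size of the dilution depends on which applies.

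**The case against.** - **Keeping the data is legitimate.** Analysing all patients as randomized, whatever insulin they received, is a recognised treatment-policy analysis. With no drug effect, rescue would be expected equally in all arms, so type I error is not inflated. This stands. The weakness is that the protocol neither states this choice nor plans an analysis that separates the drug from insulin.
- **The rule is inferred from silence, and the SAP is not at hand.** This stands in part. The protocol fixes the analysis sets, the LOCF rule and the sensitivity list, and in 12.2.6.1 defers only exploratory methodology to the SAP. A SAP could still add an analysis. A reader might infer that every efficacy analysis, PP included, is certain to keep these values. The PP deviation list is introduced as examples, so for PP this is only the likely reading.
- **Some of it is already covered.** This stands. The synopsis plans a summary of the need for additional glucose-lowering treatment, and 12.2.6.2 analyses HbA1c at Week 4, Month 2 and Month 3. On the bullets' reading, the Month 3 analysis precedes all HbA1c-triggered rescue, though not FPG-triggered rescue.
- **The power losses are assumptions.** This stands. They also use an unadjusted t-test, whereas the planned model adjusts for baseline HbA1c.
- **Setting values to missing has its own cost.** This stands. The first post-baseline HbA1c is at Visit 7 and baseline is never carried forward. An LOCF version would drop patients rescued before Visit 7, probably more of them on placebo, and would carry early values forward for others.

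**Conclusion.** The point holds as a should-fix. As written, HbA1c, FPG, SMPG and OGTT values taken on rescue insulin enter the FAS-LOCF and observed-case analyses and, on the likely reading, the PP analysis. Rescued patients can count as responders. If rescue is commoner on placebo, the contrast shrinks and power is lost; with equal rescue and equal insulin effect nothing is lost.

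The size cannot be known from the protocol. Under an assumed 30% v 10% rescue and 0.3 to 1.0 point effect, the difference is 0.64–0.50, with power 85%–64% at SD 1.4 or 97%–84% at SD 1.1. The smaller losses are more plausible if HbA1c-triggered rescue begins only after Visit 9.

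A reader might go further and infer that the primary analysis is invalid, or that a large loss of power is established. The documents do not support either. The expected bias runs against AZD1656, and the 64% figure combines the larger SD with the largest insulin effect assumed. What is at risk is interpretation: a null result or a flat response across regimens could reflect the drug or the insulin, and the stated analyses would not fully tell them apart.

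**What to change.** 1. In 12.2.6.1, state that the primary analysis uses all HbA1c values regardless of rescue (treatment policy), or name another choice. Do this before the sponsor and CRO are unblinded at the 4-month database lock (5.4.3).
2. Add one prespecified supplementary FAS analysis in which glucose-control values after the start of rescue insulin are set to missing. For HbA1c, prefer a likelihood-based repeated-measures model using Week 4, Month 2, Month 3 and Month 4. Treating baseline as part of the response would also retain patients rescued before Visit 7. OGTT has no visit between baseline and month 4, so post-rescue results there are simply left out, and the table should give the numbers.
3. In 12.2.6.2, count rescued patients as non-responders at 7% and 6.5%.
4. Show the rescue summary already planned in the synopsis by arm beside the efficacy results.
5. Reconcile the opening sentence of 5.6.1 with its cohort 1 bullets on when HbA1c above 8% triggers rescue.

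The cost is a few sentences of protocol and SAP wording and one more set of tables. The start of rescue is already in the eCRF and the sample size does not change. The downside is that the supplementary analysis rests on a missing-data assumption, which should be stated with it.
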